10.0 Statistical Considerations

Baseline variables known to be associated with parenting including age, sex, income, and marital status will be compared by treatment group using the Kruskal-Wallis test (continuous variables) or Pearson's Chi-squared test (categorical variables). We will also examine if diabetes-related variables (e.g., duration of diabetes, baseline A1C) are associated with treatment group. *A priori*, we assume that our block randomization will lead to well-balanced groups so that we will not need to control for additional confounders.

Effects of the Intervention: We will estimate the effect of the intervention on each of the continuous outcomes by fitting linear mixed-effects models developed. In modeling, outcomes will be considered at their key time-points (baseline, 3 months, 6 months, and 12 months) with treatment group and the interaction of treatment with time serving as the main explanatory variables. Such a model will allow us to test for any differences between treatment and control groups over time while accounting for baseline values. While the randomized block design should minimize confounding, we will adjust for age, income, and marital status to improve precision. The results from the adjusted and unadjusted models will be compared with respect to their estimates of the treatment effects. Our interpretation will focus on describing clinically relevant treatment effects (e.g., A1C reductions of $\geq 0.5\%$, >1 additional glucose check per day, reduction from moderate to mild depressive symptoms) with corresponding confidence intervals, rather than just significance testing. We will include a random intercept to account for within-subject correlation. The error structure of the model is assumed to be compound symmetric, and the validity of this assumption will be examined by computing Akaike Information Criteria against other common structures. Subjects will be included in the analysis if they have an outcome measured at baseline and at least one outcome measured 6 or 12 months later.

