Exploratory Aim: Examine the differential impact of intervention effects across demographic factors (i.e., marital status, income, adolescent age, and sex).

While evaluating the main effects of interventions is critical to improving health outcomes, it is equally important to examine moderators of randomized clinical trials – even those that are unsuccessful – in order to determine *for whom* interventions may work. Based on findings from the literature and our own earlier work, we will examine potential moderators, with a focus on marital status, income, and adolescent age and sex. Moderators will be tested by including an interaction term with treatment group in the regression models.

Power and sample size:

We plan to enroll 154 subjects so that, after allowing for a 15% attrition rate, 130 subjects will be available for analysis. Preliminary data from our pilot study with 30 adolescents indicates that mean A1C is 9.0% with a standard deviation of 1.16% and a correlation between repeated measurements over time of 0.60. Under these assumptions, we will have 80% power to detect a 0.5% difference in A1C if 122 subjects are measured at all 4 time points or if 138 subjects are measured only twice (out of 4 possible time points). Since we expect to obtain ≥ 3 measurements on most of subjects, enrolling 130 subjects with 2 to 4 measurements each will provide sufficient power for Aim 1. For the SCI (a measure of adherence), using preliminary data in 30 subjects we estimated baseline scores of 23.6 ± 4.2 with a correlation among repeated measures over time of 0.82. With 130 subjects measured at least twice, we will have 80% power to detect a 2.0 unit change due to treatment, which is an 8.5% difference from baseline.

Power calculations for mediation models were considered assuming 130 subjects will be available for analysis. In preliminary data, partial correlations of the mediators, PHQ9 and DFC, with A1C were 0.20 and 0.51, respectively. Correlations of the mediators with treatment were 0.52 and 0.54, respectively. Under these assumptions, we have 63% power to detect an indirect effect of treatment on A1C through PHQ9 and >99% power to detect an indirect effect of treatment on A1C through DFC. Calculations assume a 0.05 significance level.

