Power for moderation will depend on the effect size of the moderation and if the moderator is measured on a continuous or categorical scale. For continuous moderators (adolescent age), we have 80% power to detect a 0.36% change in the treatment effect on A1C per 1-sd change in the moderator. For a binary moderator (frequency 50%), we have 80% power to detect a modification of the treatment effect on A1C of 0.55%. All calculations assume $\alpha=0.05$.

Despite evidence demonstrating the effectiveness of telephone-based CBT to reduce depressive symptoms, there is a chance that mothers who receive the intervention will not report reduced depressive symptoms. If this happens, we would examine the data to determine for whom the intervention works. For example, it may be that a more limited range of scores on the screening tool (PHQ-9) predicts a better response to the intervention.

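### The moderator test does not mention time; taken literally it averages in the pre-randomization visit and estimates at most about 75% of the effect modification

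*Combined protocol and SAP*

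**What the plan says.** Three statements in section 10.0 bear on this.

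- **Main model (Effects of the Intervention).** "outcomes will be considered at their key time-points (baseline, 3 months, 6 months, and 12 months"), "treatment group and the interaction of treatment with time serving as the main explanatory variables". A random intercept is included, and "The error structure of the model is assumed to be compound symmetric", to be checked against other structures by AIC.
- **Moderators (Exploratory Aim).** "Moderators will be tested by including an interaction term with treatment group in the regression models". The moderators are marital status, income, adolescent age and sex. No visit, follow-up contrast or three-way term is named.
- **Power for moderation.** For a binary moderator with 50% frequency, "we have 80% power to detect a modification of the treatment effect on A1C of 0.55" (in % A1C). For a continuous moderator the figure is 0.36% per SD. No formula or contrast is given for either.

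Section 5.0 places all baseline data collection before random assignment.

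**The concern.** Baseline precedes randomization, so any arm difference at that visit is chance. In a model with baseline as a response, the intervention effect is what happens to the arm difference after baseline, and its modification by a moderator is a moderator-by-treatment-by-time quantity. A single moderator-by-treatment term asks something else: whether the arm difference in level, averaged over all four visits, varies with the moderator. One of those visits contributes no modification, and the chance baseline differences between the four arm-by-moderator cells go into the estimate as noise.

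The plan uses this aim to learn for whom the intervention works, even if the main effect fails, and it puts estimates with confidence intervals ahead of significance testing. An estimate that is too small in expectation undermines that use whatever its p-value. Two analysts could also follow the sentence and report different quantities.

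**Working it through.** **Inputs, all from section 10.0 unless noted.** "mean A1C is 9.0% with a standard deviation of 1.16% and a correlation between repeated measurements over time of 0.60"; "130 subjects will be available for analysis"; four visits; compound symmetry; 1:1 allocation (section 5.0); alpha 0.05. Assumptions added here: two-sided testing, a 50/50 moderator balanced across arms, and a modification of zero at baseline and constant at 3, 6 and 12 months.

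**1. The plan's main sample sizes.** The variance of a mean of m visits is SD²[1+(m−1)ρ]/m.
- m = 4: 1.3456 × 2.8/4 = 0.942.
- m = 2: 1.3456 × 1.6/2 = 1.076.

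For a 0.5% difference at 80% power, the normal approximation gives 120 and 136 subjects (rounded up to equal arms). A two-sample t-test gives 122 and 138, exactly as stated. The inputs and two-sided testing are therefore the plan's own, and its main calculation treats the effect as an arm difference averaged over the measured visits.

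**2. The literal moderator term.** Under compound symmetry and complete data it is the visit-averaged difference of differences.
- Expected value: (0+1+1+1)/4 = 0.75 of the true modification.
- SE, with four cells of N/4: 4√(0.942/130) = 0.340.
- Detectable true modification at 80% power: 2.80 × 0.340/0.75 = 1.27%.
- Per SD of a continuous moderator: half of that, 0.64%.

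An exact generalised least squares fit gives the same values.

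**3. The same modification as a 1-df contrast averaged over follow-up**, with moderator-by-visit and all other lower-order terms in the model.
- Free baseline (change from baseline): variance 1.3456 × 0.4 × 4/3 = 0.718.
- Baseline constrained equal or adjusted: variance 1.3456 × (2.2/3 − 0.36) = 0.502.

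| Test, binary moderator, N = 130 | SE | Share recovered | Detectable at 80% | Power at 0.55% |
|---|---|---|---|---|
| Literal two-way term | 0.340 | 0.75 | 1.27% | 23% |
| Follow-up average, free baseline | 0.297 | 1 | 0.83% | 46% |
| Follow-up average, baseline constrained or adjusted | 0.249 | 1 | 0.70% | 60% |

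Ratios: 1.27/0.83 = 1.53 and 1.27/0.70 = 1.83 (from unrounded values).

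**4. Sensitivity.**
- Fewer visits. The plan expects 2 to 4 measurements per subject, and its inclusion rule always requires baseline. With baseline plus two follow-ups the literal term recovers 2/3 and detects 1.46%. With baseline plus one it recovers 1/2 and detects 2.04%.
- Correlation, which comes from a 30-subject pilot. At 0.5 to 0.7 the ratio is 1.29 to 1.86 with a free baseline and 1.63 to 2.11 with baseline constrained or adjusted.
- Degrees of freedom. An overall three-way test with visit as a factor has 3 df. It detects 0.98% (free baseline) or 0.82% (adjusted), with power 31% or 43% at 0.55%. The figures in step 3 need the single-df contrast.

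**5. The plan's stated moderation sizes.** A 50/50 binary variable has SD 0.5, so at one outcome SD its detectable difference is twice the per-SD figure. The stated ratio is 0.55/0.36 = 1.53.
- 0.36 per SD is close to the baseline-adjusted follow-up contrast (0.35), and equals the figure obtained from the within-subject residual SD, 1.16√0.4 = 0.734 (0.36; binary 0.72).
- 0.55 is not reproduced. No contrast checked from a model with all lower-order terms reaches it: mean of four visits 0.95 even before dilution, change 0.83, baseline-adjusted 0.70.
- Dropping the moderator-by-visit terms gives 0.59 (free baseline) or 0.53 (constrained), but only by assuming that the moderator has no time trend of its own.

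**The case against.** The strongest reply is that the sentence is under-specified and is not a decision for a two-way term. The aim concerns differential intervention effects, and the main model carries those effects through treatment and treatment-by-time, so interacting the moderator with both is a natural reading. The main-model text also speaks of accounting for baseline values. If baseline were a covariate and only follow-up visits were outcomes, a two-way term would have no baseline dilution. Both points stand. A reader might infer that the plan has chosen the diluted test, but the documents show only that it names one term, omits time where the main-model sentence includes it, and lists baseline among the outcome time points.

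A reader might also infer that the detectable size nearly doubles. That compares a literal term in a free-baseline model with a contrast that constrains or adjusts for baseline, which the plan does not specify. Within the model as described, the increase is about 1.5-fold.

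Nor does the literal term produce excess false claims of moderation. Chance baseline differences between cells are part of its standard error, and with no moderation the test keeps its nominal 5% level.

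Finally, it cannot be shown that the stated 0.55% was meant for a different contrast from the one the sentence describes, since no formula is given and the main sample sizes do follow a visit-averaged calculation.

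**Conclusion.** The point holds as a specification fault in an exploratory aim. Followed as written, the moderator sentence gives an estimate attenuated to 75% of the true modification with four visits, 67% with three and 50% with two. It detects 1.27% A1C where a follow-up-average contrast detects 0.83% or 0.70%, that is, 1.5-fold or 1.8-fold. At 0.55%, for which the plan claims 80% power, the literal term has 23%.

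These figures rest on compound symmetry, a 50/50 moderator, SD 1.16, correlation 0.60, and a modification constant over follow-up. The detectable sizes and powers in the table also assume complete data. The harm is attenuation and lost precision. The primary comparison does not depend on the moderator term.

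**What to change.** Replace the moderator sentence with wording to this effect: moderation is tested by a single 1-df contrast, the difference between moderator levels (or per SD of a continuous moderator) in the treatment effect averaged over 3, 6 and 12 months. The contrast is taken from the longitudinal model with moderator-by-treatment-by-visit and all lower-order terms, including moderator-by-visit, and with baseline constrained equal across arms or adjusted for. Estimates by visit are descriptive.

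Restate the detectable sizes for that contrast. With complete data they are about 0.70% for a 50/50 binary moderator and 0.35% per SD for a continuous one. If a free baseline is kept, they are 0.83% and 0.42%. Give the formula, and allow for subjects with fewer than four visits.

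The cost is one or two sentences, a few more model terms and a less favourable stated figure for binary moderators. The continuous figure hardly changes if baseline is constrained or adjusted for, and no new data are needed.

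### The 2.0-unit SCI difference quoted at 80% power does not match the planned baseline-accounted mixed model, which at the plan's own inputs detects about 1.0 to 1.4 units

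*Combined protocol and SAP*

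**What the plan says.** Section 10.0, Power and sample size, gives pilot SCI scores of 23.6 ± 4.2 with a "correlation among repeated measures over time of 0.82", and then: "With 130 subjects measured at least twice, we will have 80% power to detect a 2.0 unit change due to treatment". It expresses 2.0 units as 8.5% of baseline (2.0/23.6). For A1C (SD 1.16%, correlation 0.60) it says "we will have 80% power to detect a 0.5% difference in A1C if 122 subjects are measured at all 4 time points". As a second scenario with the same power and fewer visits, it names the case in which "138 subjects are measured only twice (out of 4 possible time points"). No power method, contrast or visit is named for either outcome.

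Section 10.0, Effects of the Intervention, describes a mixed model with a random intercept over baseline, 3, 6 and 12 months, "with treatment group and the interaction of treatment with time serving as the main explanatory variables". Its purpose is to "test for any differences between treatment and control groups over time while accounting for baseline values". On the covariance: "The error structure of the model is assumed to be compound symmetric", to be checked by AIC against alternatives. Subjects enter the analysis "if they have an outcome measured at baseline and at least one outcome measured 6 or 12 months later".

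**The concern.** A correlation of 0.82 between repeated SCI scores is high. In an analysis that accounts for baseline, a high correlation removes most of the between-subject variance, so the detectable difference should be small relative to the SD. A detectable difference of 2.0 units is almost half an SD (2.0/4.2 = 0.48), close to what 130 subjects give with no use of baseline at all. This suggests that the power statement and the planned model refer to different quantities.

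Adherence is one of the two diabetes outcomes in Aim 1 (section 2.0). If the figure belongs to another contrast, the reader is misinformed about what a null SCI result would exclude. For A1C, the reader cannot tell which test carries the 80%.

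**Working it through.** **Inputs.** From Power and sample size: SCI SD 4.2, correlation ρ = 0.82; A1C SD 1.16, ρ = 0.60, difference 0.5; N = 130; α = 0.05. Equal allocation is from section 5.0, and compound symmetry from Effects of the Intervention. Assumed here: two-sided α. The planned covariates are left out because the documents give no R² for them.

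**Method.** Two-sample comparison with variance f × SD², by noncentral t (except the 3-df test, by noncentral chi-square). As an approximation, detectable difference ≈ 2.80 × SD × √(4f/N); the t version is about 1% larger.

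**Step 1: reproduce the plan's figures.** For a level averaged over m visits, f = (1 + (m−1)ρ)/m.
- A1C, m = 4: f = (1 + 1.8)/4 = 0.70, giving N = 122 (stated 122).
- A1C, m = 2: f = 1.6/2 = 0.80, giving N = 138 (stated 138).
- SCI, m = 2: f = 1.82/2 = 0.91. At N = 130, 2.80 × 4.2 × √(3.64/130) = 1.97, or 1.98 by t; power for 2.0 is 80.6% (stated 2.0 at 80%).

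Among the contrasts tried under compound symmetry, only this one reproduces all three figures. That the plan used it is an inference, since no method is stated. In this formula a higher ρ raises f and costs sensitivity. Every analysed subject must have a baseline value, so for a subject with two measurements one of them precedes treatment. An averaged difference of 2.0 then corresponds to about 4 units at follow-up.

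**Step 2: the planned model, SCI, N = 130, ρ = 0.82, all subjects seen at the tested visits.**

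| Contrast | f | Detectable at 80% | Power for 2.0 |
|---|---|---|---|
| Change to one visit, 2(1−ρ) | 0.36 | 1.25 | 99.4% |
| Follow-up adjusted for baseline, 1−ρ² | 0.328 | 1.19 | 99.7% |
| Linear slope over 0, 3, 6, 12 months, at 12 months, 144(1−ρ)/78.75 | 0.329 | 1.19 | 99.7% |
| Mean of three follow-ups minus baseline, (1+2ρ)/3 − 2ρ + 1 | 0.24 | 1.02 | above 99.9% |
| 3-df treatment-by-time test, effect growing linearly | – | 1.40 | 98.7% |

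For the first row, 2.80 × 4.2 × √(1.44/130) = 1.24, or 1.25 by t. That is 5.3% of 23.6, and 2.0 units would need 52 subjects. Simulating the random-intercept model with four complete visits and testing the 12-month interaction gave power 0.797 at 1.25 units (600 runs) and 0.99 at 2.0 (300 runs).

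**Step 3: departures from those conditions (assumptions; the documents give no figures).**
- *Some subjects lack the tested visit.* Suppose each subject has baseline plus only one of 6 or 12 months, and a proportion p has the 12-month value. For the 12-month contrast, f = (1−ρ)² + (1−ρ²)/p. With p = 0.8, f = 0.0324 + 0.4095 = 0.442, detecting 1.38; p = 0.7 gives 1.47; p = 0.5 gives f = 0.688 and 1.72.
- *Correlation decays.* Under AR(1) by visit order with adjacent correlation 0.82, the baseline-to-12-month correlation is 0.82³ = 0.55. Then f = 0.90, and the single-visit change detects 1.97.
- *Pilot uncertainty in ρ.* With 30 subjects, a Fisher 95% interval for ρ is 0.65 to 0.91, giving 1.73 to 0.88. At 0.65, power for 2.0 is still about 90%. With the SD also at its upper 95% limit (5.65), the figure is 2.33.

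**Step 4: A1C.** At ρ = 0.60, (1+ρ)/2 and 2(1−ρ) both equal 0.80, so 138 fits either the average or the change. The 122 is nearly matched by a slope (126, or 124 with equally spaced visits). Power for 0.5% at N = 130 is 78% for a single-visit change, 81% for a slope and 92% for the mean of three follow-ups minus baseline.

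**The case against.** The 2.0 is not an arithmetic slip: it follows from its inputs by a recognised formula that also gives 122 and 138. The planned model contains a treatment term, no single deciding test is named, and averaging two follow-up visits without baseline would also give 1.98. This stands as far as the arithmetic goes. It does not rescue the figure, because neither average is the baseline-accounted comparison that the section describes.

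Any single replacement also depends on a contrast that the reviewer chooses. The 1.25 needs all 130 subjects at the same follow-up visit and compound symmetry, which the plan treats as provisional. This stands. Under AR(1) the change contrast returns almost exactly to 2.0, although the plan's single correlation of 0.82 describes no decay.

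Finally, the figure is cautious, sample size is argued mainly through A1C, and interpretation is to rest on clinically relevant effects with confidence intervals. This limits the consequence, but the plan does not present 2.0 as a cautious choice.

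A reader might infer that the trial is underpowered, or that the A1C calculation is wrong. The documents support neither. For SCI the mismatch runs in the safe direction, and the A1C numbers are compatible with more than one contrast.

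**Conclusion.** The concern holds as a mismatch between the power statement and the planned model. At the stated SD and correlation, under compound symmetry, with two-sided 5% and complete data at the tested visit, the planned analysis detects about 1.0 to 1.4 SCI units, not 2.0. For a single-visit change the stated figure is 1.6 times too large (2.0/1.25). Missing visits could bring the detectable difference to about 1.4 to 1.7, and decaying correlation to about 2.0. These are assumed scenarios, not the plan's stated inputs. Enrolment and analysis are unaffected. For A1C the gap is only that the 80% is attached to no named contrast.

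**What to change.** Name the power method, the deciding treatment-by-time contrast and its visit for SCI and A1C. Treat baseline as pre-treatment, and replace the 2.0 (8.5%) figure accordingly. If a single-visit change is chosen, the SCI sentence could read:

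*80% power to detect a between-group difference in change of about 1.25 units (5.3% of 23.6) with 130 subjects measured at baseline and at the same follow-up visit, assuming compound symmetry with correlation 0.82.*

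Add that the figure rises to about 1.4 to 1.7 if only 80% to 50% have the 12-month value, and to about 2.0 if correlation decays as AR(1) (baseline-to-12-month correlation 0.55). Alternatively, keep 2.0, label it as deliberately cautious, and give its power under the planned model (about 99% at correlation 0.82, about 90% at 0.65).

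State A1C power for the same contrast: 78% for 0.5% at N = 130 (detectable 0.51%) for a single-visit change. Recompute the 122 to match: 124 to 126 for a slope, 94 for the mean of three follow-ups minus baseline, 138 for a single-visit change.

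The cost is one reworded paragraph. The only drawback is a slightly less favourable A1C figure if the single-visit change is chosen.

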2.0 Rationale and Specific Aims

Based on the Transactional Stress and Coping Model, which views chronic illness as a stressor to which children and mothers attempt to adapt, the ways in which mothers cope with the stress of diabetes play an important role in both maternal and adolescent adjustment to the disease. The proposed study is based on the premise that, by reducing mothers' depressive symptoms and improving the quality of parental involvement, we will improve outcomes in adolescents with T1D. Building on effective interventions to treat depression in adults, and our own pilot work in this population, the proposed study will use a rigorous approach to evaluate the efficacy of a cognitive-behavioral intervention for mothers of adolescents with type 1 diabetes to promote the use of adaptive coping strategies and positive parenting practices.

The specific aims of this project are:

1. Evaluate the efficacy of the Communication & Coping intervention as compared to an attention control condition on adolescents' diabetes outcomes (i.e., glycemic control, adherence) over 12 months. We will examine whether these effects were driven by the targeted mediators (maternal depressive symptoms, parental involvement).

Hypothesis: The adolescents of mothers who receive the intervention will demonstrate better glycemic control and better adherence to treatment than those in the attention control condition.

2. Evaluate the efficacy of the Communication & Coping intervention as compared to an attention control condition on adolescents' psychosocial outcomes (i.e., adolescent depressive symptoms and quality of life) over 12 months.

Hypothesis: The adolescents of mothers who receive the intervention will report better quality of life and fewer depressive symptoms than those in the attention control condition.

Exploratory Aim: Examine the differential impact of intervention effects across demographic factors (i.e., marital status, income, adolescent age, and sex).

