3.0 Animal Studies and Previous Human Studies

[name] and colleagues conducted a pilot study of the communication & coping intervention with 30 mothers of adolescents with type 1 diabetes, which supported the feasibility and initial efficacy of the intervention (<http://psycnet.apa.org/record/2018-09864-003>). Results from our pilot study indicated significant intervention effects on adolescents' quality of life and depressive symptoms. In addition, adolescents whose mothers received the intervention demonstrated promising improvements in glycemic control, and we found support for the effect of the intervention on mediating variables, with large effects on maternal depressive symptoms and family conflict.

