6.0 Study Procedures

At baseline, 3 months, 6 months, and 12 months, mothers and adolescents will complete surveys consisting of measures are widely validated and have been used successfully by our research team in previous studies. Follow-up data will be collected at regularly-scheduled diabetes clinic visits, so that questionnaire data corresponds with clinical data. The measures take about 40 minutes to complete. Mothers will also complete a measure of depression (PHQ-9) via a link emailed to them by the study team biweekly during the active phase of the intervention (first 3 months). All measures will be collected using REDCap.

Demographics - completed by mother

Responses to Stress Questionnaire (RSQ) measures 3 coping factors: primary control coping, secondary control coping, and disengagement coping - completed by mother

Multidimensional Scale of Perceived Social Support (MSPSS) - completed by mother

Patient Health Questionnaire - 9 items (PHQ-9)-completed by mother

Generalized Anxiety Disorder Scale - 7 items (GAD-7) completed by mother

Diabetes Family Conflict Scale (DFCS) - completed by mother and adolescent

Self-Care Inventory (SCI) - completed by mother and adolescent

Pediatric Quality of Life Inventory (Peds-QL) diabetes-specific module - completed by adolescent

Child Behavior Checklist (CBCL) - completed by mother

Youth Self Report (YSR) - completed by adolescent

Problem Area in Diabetes - Teen (PAID-T) - completed by adolescent

Parent Diabetes Distress Scale (PDDS) - completed by mother

Collaborative Parent Involvement Scale - completed by adolescent

Revised Brief Diabetes Knowledge Test - completed by mother

COVID-19 Questions – completed by mother and adolescent

Satisfaction Survey – completed by mother at 3 month follow-up

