Examining mediators will provide evidence for the mechanisms of change, offering direction for program implementation and future research. Investigating mediators of the intervention also allows us to test the theoretical basis and the effect of intervention on separate outcomes,¹⁰⁷ such as glycemic control, and psychosocial outcomes. To assess direct and indirect effects of potential mediator variables, we will follow the steps outlined by MacKinnon and colleagues^{108,109} to establish mediation. The bootstrap method will be used to obtain a 95% confidence interval for the total, direct, and indirect effects. We will test maternal depressive symptoms and parental involvement as mediators of treatment effects, maintaining consistent temporal ordering, by considering baseline randomized treatment, 3-month depressive symptoms and parental involvement variables as the mediators, and 6-month outcomes (treatment effects), as well as 12-month outcomes (sustained treatment effects). Our longitudinal data will also allow us to consider additional analyses that account for the bidirectional relationships between family functioning and depressive symptoms.

To determine the feasibility of the intervention, we will examine recruitment and retention data. In addition, fidelity checks will be conducted by reviewing 20% of the telephone sessions, which will be coded for content by an independent rater. We propose a feasibility benchmark of $\geq 90\%$ fidelity. To evaluate acceptability of the intervention, we will examine participation (phone call attendance), adherence (completion of homework), and satisfaction ratings. We propose a feasibility benchmark of $\geq 80\%$ attendance. We will also conduct exit interviews with mothers, which will be analyzed with a content analysis approach to identify themes across participants.

[figure not shown]
Assessing biases caused by dropouts: Some subjects may not return for their follow-up visit and hence have missing values of their response variables. Frequently, such subjects ("dropouts") are not a random sample of the entire cohort and an analysis of only the complete cases will bias the results. Indirect information about the nonrandom dropouts will be obtained by using binary logistic regression to predict dropout status on the basis of all baseline predictor variables.

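### The mediation model as stated names no baseline mediator or baseline outcome, so stable differences between families could be reported as mediation

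*Combined protocol and SAP*

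**What the plan says.** Aim 1 (section 2.0) asks whether effects on diabetes outcomes run through the "targeted mediators (maternal depressive symptoms, parental involvement". The mediation paragraph of section 10.0 repeats the pair: "We will test maternal depressive symptoms and parental involvement as mediators of treatment effects". It gives the time order as treatment at baseline, then "3-month depressive symptoms and parental involvement variables as the mediators, and 6-month outcomes (treatment effects", with 12-month outcomes for sustained effects. It refers to cited steps for establishing mediation and plans a bootstrap 95% interval. It lists no baseline covariates.

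The paragraph on effects of the intervention, also in section 10.0, says its mixed-effects model will "test for any differences between treatment and control groups over time while accounting for baseline values" and adjusts for age, income and marital status. Both statements concern the treatment-effect models only.

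Under power and sample size, the plan says: "In preliminary data, partial correlations of the mediators, PHQ9 and DFC, with A1C were 0.20 and 0.51, respectively". Correlations of the same two mediators with treatment are 0.52 and 0.54. At 130 subjects and a 0.05 level, the stated power is 63% through PHQ9 and more than 99% through DFC.

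**The concern.** Randomisation makes the arms comparable, so the effect of treatment on the mediator is protected. It does not make mothers with low and high 3-month depressive symptoms comparable within an arm. A family whose mother has long had more symptoms may also have long had a higher A1C, for reasons that the 3-month score did not cause. Measuring the mediator before the outcome does not remove this, because a stable difference precedes both.

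Treatment is expected to move the mediator strongly, so any within-arm association between mediator and outcome is enough to make the indirect effect significant. The trial could then report that its benefit works through maternal depressive symptoms when it does not. Section 10.0 says the mediation results are meant to guide implementation and later research.

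**Working it through.** **Inputs.** From the power section: N = 130; treatment–mediator correlation 0.52 (PHQ9); mediator–A1C partial correlation 0.20 (PHQ9) and 0.51 (DFC); A1C correlation over time 0.60; level 0.05, taken as two-sided. Assumed: mediator correlation over time 0.60 (0.4 and 0.8 are used for the power cost). The plan gives no value for this.

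**1. The plan's own figures.** Mediation is declared when both paths are significant. For a partial correlation p with k covariates besides the mediator, z = atanh(p) × √(127 − k) and power = Φ(z − 1.96) + Φ(−z − 1.96).
- Treatment to PHQ9: atanh(0.52) × √127 = 6.50, power above 99.9%. The second path therefore decides.
- PHQ9 to A1C, k = 1: 0.2027 × √126 = 2.276, power 62.4%. The plan states 63%.
- DFC to A1C, k = 1: 0.5627 × √126 = 6.32, power above 99.9%. The plan states >99%.

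Both figures reproduce.

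**2. False mediation.** Let mediator and A1C each be a stable trait plus independent error, with no effect of mediator on A1C. Let r be the within-arm correlation due only to the traits. With stability 0.60 for both, the mediator–A1C partial correlation is:
- treatment only (k = 1): r
- plus baseline A1C (k = 2): (r − 0.6r) / √[(1 − r²)(1 − 0.36)] = 0.5r / √(1 − r²)
- plus baseline A1C and baseline mediator (k = 3): 0.16r / (0.64 − 0.8r²) = 0.25r / (1 − 1.25r²)

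At r = 0.20 these are 0.200, 0.102 and 0.053; z is 2.276, 1.145 and 0.587; the chance of a significant path is 62.4, 20.9 and 9.0%. Simulation of the joint test (6,000 trials per cell) agrees:

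| Non-causal r | No baseline terms | Baseline A1C only | Both |
|---|---|---|---|
| 0.05 | 9% | 6% | 5% |
| 0.10 | 21% | 9% | 6% |
| 0.15 | 40% | 13% | 7% |
| 0.20 | 63% | 21% | 9% |

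At r = 0.20, the percentile bootstrap of the indirect effect gave 65, 21 and 9% (500 trials). At r = 0 all three models stay near 5%.

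**3. What adjustment does to power.** Now let the 0.20 be wholly causal and not already baseline-adjusted. With both baseline terms and mediator stability s, the partial correlation is 0.20√(1 − s²) / √[0.04(1 − s²) + 0.60], where 0.60 = 1 − 0.04 − 0.36. For s = 0.4, 0.6 and 0.8 this is 0.230, 0.202 and 0.153, and power is 74, 63 and 40%. Simulation gives 74, 61 and 40%, against about 63% with no baseline terms.

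**4. Which mediators the power figures cover.** Section 6.0 identifies the PHQ-9 as the depression measure, so the 63% belongs to a named mediator. DFC is not spelled out. The matching instrument is "Diabetes Family Conflict Scale (DFCS) - completed by mother and adolescent", which section 6.0 lists separately from the Collaborative Parent Involvement Scale. No section links the two, and the plan gives no correlation of the involvement scale with treatment or A1C.

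**The case against.** The strongest reply is that this argues from silence. The mediation paragraph defers to cited steps that it does not reproduce, and section 10.0 contains a figure not shown. Either could include baseline terms. The paragraph also calls the 6-month outcomes treatment effects, which elsewhere in section 10.0 are estimated with baseline values accounted for. A reader might infer that the team will leave baseline out. The documents do not support that; they show only that the terms are not stated. If baseline A1C alone is intended, the 0.20 row gives 21%, not 63%.

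A second reply concerns size. A reader might take the rates to be far higher still, since a larger non-causal correlation would push them above 63%. For PHQ9 the plan's whole correlation is 0.20, so nothing above that row is anchored; the larger value, 0.51, belongs to DFC. Even the 0.20 row requires all of the correlation to be non-causal. The plan also does not say what its partial correlations were adjusted for. If baseline was already removed, neither that benchmark nor the power figures in step 3 apply. With the partial correlation held at 0.20, two added terms move power only from 62.4% to 61.7%.

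On DFC, a reader might infer that the >99% is wrong or that the wrong mediator was powered. The arithmetic is right. Section 3.0 reports an "effect of the intervention on mediating variables, with large effects on maternal depressive symptoms and family conflict", and the mediation paragraph mentions "bidirectional relationships between family functioning and depressive symptoms". DFC may have been meant as the involvement indicator; the plan does not say so.

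What stands is that the adjustment set is unstated where randomisation gives no protection, and one sentence would settle it.

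**Conclusion.** The concern holds for the mediation model as stated. Without baseline terms, the chance of false mediation through PHQ9 runs from about 9% to 63% as the non-causal part of the correlation goes from 0.05 to 0.20. With both terms it runs from about 5% to 9%. This rests on the trait-plus-error model, mediator stability of 0.60, and a pilot correlation not already adjusted for baseline. Baseline A1C alone closes only part of the gap.

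The DFC mismatch is minor and mainly a matter of labels: the >99% is not tied to a mediator that Aim 1 or the mediation paragraph names.

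A reader might infer that the trial's main result is in doubt. It is not. Only the mediation question within Aim 1 is affected.

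**What to change.** In the mediation paragraph of section 10.0, state that both regressions (treatment on the 3-month mediator; treatment and mediator on the 6- and 12-month outcome) include the baseline mediator and the baseline outcome. Add that indirect effects are interpreted assuming no remaining mediator–outcome confounding. If the cited steps already include these terms, say so.

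Under power and sample size, say what the partial correlations were adjusted for and qualify the 63%.

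For DFC, either state that the DFCS is the parental-involvement indicator, or add family conflict as a prespecified mediator in section 2.0 and in the mediation paragraph. Unless the DFCS is the involvement measure, say that power for the parental involvement scale is not established.

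The cost is wording: surveys and A1C are already planned at baseline. The real price is power if the mediator is very stable (about 40% at stability 0.8, under the assumptions in step 3). Some false mediation also remains with both terms, about 9% in the 0.20 row.
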